9.9.2 Adverse Events

Treatment-emergent AEs are AEs that occur during the treatment phase or a pre-existing medical condition that worsened in intensity during the treatment phase. Treatment-emergent AEs will be summarized overall and tabulated by system organ class and preferred term using the latest available Medical Dictionary for Regulatory Activities dictionary. The total number of subjects reporting at least 1 AE, the percentage of subjects with an AE, and the number of events reported will be presented.

Summary tables will be prepared for:

- All treatment-emergent AEs
- Treatment-emergent AEs by causality (related/unrelated)
- Treatment-emergent AEs leading to death
- Treatment-emergent AEs by intensity
- Treatment-emergent SAEs
- Treatment-emergent AEs leading to discontinuation
- Treatment-emergent AEs with an incidence of at least 5%
- Non-serious treatment-emergent AEs with an incidence of at least 5%

Furthermore, the overall AE summary table by system organ class and preferred term will also be produced for the study phase, suppression phase, and the stimulation phase for the ES and safety cohorts.

A separate AE listing will be provided for the screening phase, suppression phase, stimulation phase, and treatment phase of the trial.

9.9.2.1 Treatment-Emergent AEs of Special Interest

Standardized criteria will be applied to some AEs of special interest to establish intensity/grade. For AEs associated with vaginal bleeding/spotting, vaginal pain and irritation, and vaginal or cervical abrasions and lesions, standardized criteria will be used by the sites to record the intensity of these AEs (see section 8.3 and [Appendix 2](#), [Appendix 3](#), and [Appendix 4](#)). For these AEs and AEs associated with vaginal haemorrhage, vaginal infection and vaginal adhesions, a summary table of the treatment-emergent AEs of special interest will be produced by preferred term, grade (intensity), and seriousness for subjects in the safety cohort for the treatment phase and the study phase.

9.9.3 Safety Laboratory Variables

For each laboratory parameter (hematology, chemistry, and urinalysis), the number of subjects with abnormal laboratory values will be summarized for the study phase and the stimulation phase for the

ES and safety cohorts. This summary will also be produced for the treatment phase for the safety cohort.

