There are 3 analysis cohorts for this trial. The mITT cohort consists of all subjects who had successful oocyte retrieval, received at least 1 dose of IMP, and had completed fresh embryo transfer. The safety cohort comprises all subjects treated with IMP. The eligible subjects (ES) cohort consists of all subjects who were deemed eligible for trial participation based on inclusion and exclusion criteria at screening and treated with oral contraceptives, leuprolide acetate, or MENOPUR.

The primary objective is to estimate the cumulative rate of any spontaneous abortion, including spontaneous clinically recognized pregnancy loss and blighted ovum during the trial (up to Week 12 following oocyte retrieval) for subjects in the mITT cohort. The number and rates of any spontaneous abortions will be summarized and associated exact 95% confidence intervals will be generated. Furthermore, as part of a Bayesian sensitivity analysis, a 95% credible interval will be generated. The spontaneous abortion rate, biochemical abortion rate, clinical pregnancy rate, and positive β -hCG rate will be similarly analyzed for the mITT and safety cohort, for subjects that had oocyte(s) retrieved. However, for these endpoints, credible intervals will not be derived. Furthermore, safety will be assessed by summarizing treatment-emergent AEs for the safety and ES cohorts. Treatment-emergent AEs will be summarized overall, by grade (intensity), seriousness, and drug relatedness by system organ class and preferred term using the Medical Dictionary for Regulatory Activities. A treatment-emergent AE is any AE that occurs after the start of PVR and through the end of the trial, or a pretreatment AE/medical condition that worsens in intensity after the start of PVR. Furthermore, a separate treatment-emergent AE summary table will be generated for AEs of special interest, such as vaginal pain and irritation, vaginal infection, vaginal bleeding/spotting, vaginal hemorrhage, vaginal adhesions and vaginal or cervical abrasions and lesions. These events will also be further analyzed by grade (intensity). Tolerability for the safety cohort will be assessed by summarizing the total number of subjects who prematurely discontinued PVR and the associated reasons for discontinuation. This summary will be based on the safety cohort.

For the safety and ES cohorts, the number of subjects with abnormal clinical laboratory and vital sign assessments will be summarized.

TABLE OF CONTENTS

SYNOPSIS.....	2

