## Secondary Endpoints

- Cumulative rate of spontaneous abortions determined at 6 and 10 weeks post-oocyte retrieval in all subjects treated with PVR.
- Cumulative rate of biochemical abortions determined at 6 and 10 weeks post-oocyte retrieval in all subjects treated with PVR. Biochemical abortion is defined as a positive  $\beta$ -hCG test at 2 weeks and 2 weeks + 3-4 days post-oocyte retrieval, but followed by no observed gestational sac on a later TVUS, or followed by a negative  $\beta$ -hCG test.
- Rate of ectopic and heterotopic pregnancies in all subjects treated with PVR following oocyte retrieval.
- Rate of abnormal findings in clinical laboratory tests and vital signs for all subjects treated with PVR.
- Frequency, intensity/grade, seriousness, and relatedness of adverse events (AEs) for all subjects treated with PVR.
- Frequency, intensity/grade of vaginal bleeding/spotting, vaginal hemorrhage, pain, vaginal infection, and vaginal irritation for all subjects treated with PVR.
- Frequency, intensity/grade, seriousness, and relatedness of AEs associated with vaginal and cervical abrasions and lesions and with vaginal adhesions for all subjects treated with PVR.
- Frequency and reason for PVR discontinuation.
- Positive  $\beta$ -hCG rate (positive serum  $\beta$ -hCG test) at 2 weeks and 2 weeks + 3-4 days post-oocyte retrieval in all subjects treated with PVR.
- Clinical pregnancy rate (TVUS showing at least 1 intrauterine gestational sac with fetal heartbeat) at 6 and 10 weeks post-oocyte retrieval in all subjects treated with PVR.

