#### 10.3.2 Laboratory Variable Shift Tables

Changes relative to normal ranges are presented with shift tables with total number of subjects, and number and percent of subjects who experienced a shift from baseline to their end of trial visit. The following categories for shift tables are defined:

- Low: Values which are below the lower reference range limit;
- Normal: Values which are within the lower and upper reference range;
- High: Values which are above the upper reference range limit.

For all hematology and clinical chemistry variables, shift tables will be prepared to show all shifts. More specifically, for hematology and clinical chemistry, tables presenting the changes from *Low* or *Normal* to *High* and from *High* or *Normal* to *Low* will be provided.

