#### 10.3.4 Urinalysis

Urinalysis parameters will be summarized by visit for the ES and safety cohorts. For continuous variables, mean, standard deviation, median, minimum and maximum will be used to summarize the assessment. In contrast, for categorical parameters, percentages and frequencies will be used. Furthermore, for each urinalysis parameter the number of subjects with abnormal laboratory values will be summarized by visit for the ES and safety cohorts.

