## 12 Deviations from Protocol

The following changes and additions from the planned displays and analyses described in the previous version of the clinical trial protocol have been implemented in the statistical analysis plan:

- All 90% confidence intervals have been replaced with 95% confidence intervals based on FDA input on the statistical analysis plan.
- The embryo quality analysis that is described in this SAP was not mentioned in the clinical trial protocol.
- The definition of the Eligible Subjects cohort is taken to be a subject that has received at least one dose of oral contraceptives, leuprolide acetate, and MENOPUR. This aligns with the analogous cohort from the DR-PGN-302 study. In the clinical trial protocol, an “or” is used instead of an “and”.

These revisions have been implemented in the clinical trial protocol version 6.0.

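### For blood tests the SAP replaces the protocol's count of women with abnormal values with baseline-to-last-value shift tables, so no treatment-phase abnormality rate is tabulated

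*Protocol*

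**What the plan says.** Both documents carry the same secondary endpoint. In SAP 2.2 it reads "Rate of abnormal findings in clinical laboratory tests and vital signs for all subjects treated with PVR".

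The protocol has one analysis that matches it. Section 9.9.3 says "For each laboratory parameter (hematology, chemistry, and urinalysis), the number of subjects with abnormal laboratory values will be summarized", for the study and stimulation phases in the ES and safety cohorts and for the treatment phase in the safety cohort. The synopsis repeats the plan for those two cohorts: "the number of subjects with abnormal clinical laboratory and vital sign assessments will be summarized".

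The SAP, written against protocol version 6.0, treats the three laboratory groups differently.

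- **Hematology and chemistry.** SAP 10.3.1 gives observed values and changes from baseline. SAP 10.3.2 gives Low/Normal/High shift tables: "For all hematology and clinical chemistry variables, shift tables will be prepared to show all shifts", reported as "number and percent of subjects who experienced a shift from baseline to their end of trial visit". SAP 10.3.3 lists every subject with an abnormal value at any time-point.
- **Urinalysis.** SAP 10.3.4 has the only explicit laboratory count of abnormal subjects: "for each urinalysis parameter the number of subjects with abnormal laboratory values will be summarized by visit for the ES and safety cohorts".

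SAP 10.3 sets the laboratory baseline at Visit 4 and takes the last post-baseline observation as end of trial.

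**The concern.** The endpoint is a rate of abnormal findings in treated women. The natural estimator, and the one the protocol states, is the number of women with an abnormal value during a phase. A shift table that uses one follow-up value answers a different question: how many women were abnormal at the last sample.

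The difference matters because of when that last sample is taken. Visit 10 is scheduled two weeks after the last exposure to the ring. Visit 9, or the Early Withdrawal visit within a week of the last dose, is the post-ring blood sample closest to exposure. For a woman with both, the SAP's only categorical blood result is the later one. An abnormality that resolves once the ring is stopped is therefore the kind this table would miss, and a reader could take the shift proportion as the endpoint's rate.

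**Working it through.** There is no plan figure to reproduce. The check compares the texts and then makes one small calculation with assumed rates.

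**1. Planned categorical summaries, side by side**

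| Laboratory group | Protocol 9.9.3 | SAP 10.3 |
|---|---|---|
| Hematology | Women with abnormal values, by phase | Shift, Visit 4 to last value; listing |
| Chemistry | Women with abnormal values, by phase | Shift, Visit 4 to last value; listing |
| Urinalysis | Women with abnormal values, by phase | Women with abnormal values, by visit; listing |

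The explicit count covers three of three groups in the protocol and one of three in the SAP. Even that one changes from by phase to by visit. Of the safety tests in Protocol 7.2.6, leaving out the hormone assays, 10 are chemistry, 6 hematology (counting the differential as one) and 6 urinalysis. So 16 of 22 have no explicit count of abnormal subjects in the SAP.

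**2. Samples that feed the shift table**

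Protocol 7.2.6 schedules chemistry and hematology at screening and Visits 4, 9 and 10. With Visit 4 as baseline, two scheduled post-ring samples remain. Protocol 3.5.6 asks women who stop early to have both an Early Withdrawal visit and an End-of-trial visit, so two samples are planned for them as well. The four possible patterns are:

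| Visit 9 / Early Withdrawal | Visit 10 | End value in shift table | Abnormal at any time after the first ring |
|---|---|---|---|
| Normal | Normal | Normal | No |
| Normal | Abnormal | Abnormal | Yes |
| Abnormal | Abnormal | Abnormal | Yes |
| Abnormal | Normal | Normal | **Yes** |

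Only the last row differs. Hence:

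any-time rate − end-of-trial rate = P(abnormal at the earlier visit and normal at Visit 10).

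**3. Size**

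The documents give no abnormality rates, so the following are assumptions. Let the chance of an abnormal value be p at each visit.

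- If every earlier abnormality persists to Visit 10, the difference is 0.
- If the two visits are independent, the any-time rate is 1 − (1 − p)². For p = 5% this is 1 − 0.95² = 9.75%, a difference of 4.75 points. For p = 10% it is 1 − 0.90² = 19%, a difference of 9 points.

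Two samples about two weeks apart in one woman are unlikely to be independent. These figures only show the direction and what the size depends on.

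**4. The stimulation phase**

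This phase ends the day before the first ring, and no chemistry, hematology or urinalysis sample is scheduled between screening and Visit 4. Omitting that part of 9.9.3 loses little.

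**The case against.** A reader might infer that the SAP estimates no abnormality rate for any blood test, or that the endpoint will be reported for urine and not for blood. The documents do not support either. The shift tables cover every hematology and chemistry variable with numbers and percentages. If all shifts are shown as a full cross-table, they give the proportion abnormal at baseline and at the last value. The urinalysis plan is not the protocol's count either: "for each urinalysis parameter the number of subjects with abnormal laboratory values will be summarized by visit" gives no any-time rate.

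A reader might also infer from SAP 12 that the count was dropped without disclosure. That section is introduced with "The following changes and additions from the planned displays and analyses", but the sentence goes on to refer to the previous protocol version, and the section ends by saying that version 6.0 has taken the revisions in. It does not claim to list differences from version 6.0, so its silence shows little. No SAP sentence withdraws the 9.9.3 count.

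The consequence is also limited. Laboratory abnormalities judged clinically significant are adverse events and enter those tables. Every abnormal value is listed. Blood values are described at each time-point. The endpoint is descriptive, and both documents say the ranking of endpoints is for prioritising, not for judging success.

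All of this stands, but it does not close the gap. Protocol section 9 leaves the detail of the analysis to the SAP, so a programmer working from SAP 10.3 would not produce the 9.9.3 table. A listing gives no rate. Adverse event tables capture only what the investigator judged significant. For vital signs, the other half of the same endpoint, SAP 10.3.5.2 does count women with one or more notable treatment-emergent values, so an any-time count is already within the SAP's practice.

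**Conclusion.** The protocol and SAP disagree on how a named secondary safety endpoint is summarised. For hematology and chemistry, a shift from Visit 4 to the last value stands in for the count of women with abnormal values by phase. For urinalysis, counts by visit do so. No any-time treatment-phase abnormality rate is tabulated for any laboratory parameter. For a woman with both post-ring blood samples, the categorical result comes from about two weeks off the ring.

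The shift tables cannot overstate the any-time rate. They understate it by the share of women abnormal at Visit 9 or Early Withdrawal and normal at Visit 10. That share cannot be derived from the documents and is zero if abnormalities persist. The conclusion assumes that samples are taken as scheduled and that the tables follow SAP 10.3 as written. The primary analysis is unaffected. The point is still worth correcting, because the trial is to be assessed on the whole of its safety data and the correction is small.

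**What to change.** In SAP 10.3, reinstate the 9.9.3 summary:

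- For each hematology, chemistry and urinalysis parameter, give the number and percentage of safety-cohort women with at least one value outside the reference range after the first ring (treatment phase). The denominator is women with at least one post-ring value. State that the Visit 4 sample, which is the SAP's baseline, is not counted as post-ring.
- Add the study-phase summary for the ES and safety cohorts, as 9.9.3 specifies. For the stimulation phase, a sentence noting that no sample is scheduled would do.
- Keep the shift tables and the by-visit urinalysis counts as support.

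Splitting low from high and adding a column for clinically significant values are optional; 9.9.3 does not ask for them. If the sponsor prefers the shift tables alone, the SAP should state this as a departure from 9.9.3 and say that they describe the last value only.

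The cost is a few lines of SAP text and one table layout, using data already collected. Visits, sample size and the primary analysis do not change.

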9.9.4 Vital Signs

For each vital sign parameter, the number of subjects with abnormal vital signs will be summarized for the study phase and stimulation phase for the ES and safety cohorts. This summary will also be produced for the treatment phase for the safety cohort.

9.9.5 Bleeding Log

At the start of PVR, each subject will receive a bleeding log (see section [8.3](#) and [Appendix 4](#)). For each incidence of sanitary napkin use for bleeding/spotting, subjects will be instructed to record the date, time of day, and the severity of the bleeding. For each subject, for each day: the grade (intensity) of bleeding associated with each sanitary napkin use will be summed. The sum of the daily grades (intensity) of bleeding will be averaged by visit window where the visit window will cover the subject's Bleeding Log recording period (i.e., from the start of the PVR to the End-of-trial visit). Finally, this subject data will be summarized across all subjects for the safety cohort by visit window. The summary will include mean, median, standard deviation, minimum and maximum. Furthermore, this analysis will be repeated removing the periods associated with AEs reported as vaginal hemorrhage, the primary endpoint of spontaneous abortion, the secondary endpoint of biochemical abortion and information collected after the cessation of the use of PVR.

9.9.6 Vaginal Hemorrhage

The number of subjects with vaginal hemorrhage (see Sections [7.2.5](#) and [8.3.6](#)) will be summarized for the safety cohort.

9.9.7 Pelvic Examination

A pelvic examination will be performed at screening, Visits 4, 7P, 8, 9, and 10 to document the presence and grade (intensity) of any pain, irritation, abrasions, or lesions on the cervix or vagina using standardized criteria, and the presence and grade (intensity) of any vaginal adhesions using standardized criteria ([Appendix 2](#)). If any lesions or abrasions are found on the cervix or vagina or vaginal adhesions are noted, another examination will be performed 2-4 days later. The grade (intensity) for each type of assessment will be summarized by visit for the safety cohort. Furthermore, a shift table will be presented summarizing the change in grade (intensity) from Visit 4 to the End-of-trial, where the End-of-trial is defined to be the last assessment in the treatment phase.

An associated listing will also be produced.

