17. History of more than 1 failed fresh IVF cycle. *Note:* an ART cycle is started when a woman begins taking medication to stimulate the ovaries to develop eggs or, if no drugs are given, when the woman begins ovarian follicular monitoring (using ultrasound or blood tests) for natural egg production ([Centers for Disease Control, 2005](#)). A failed cycle is defined as having started a cycle and not becoming pregnant or pregnancy loss prior to the 20th week of pregnancy.
18. More than 2 consecutive clinical miscarriages (gestational sac observed on ultrasound).
19. Insulin-sensitizing agents, ART cycle, or ovarian stimulation with gonadotropins within 30 days or clomiphene stimulation within 90 days prior to the screening FSH and estradiol blood draw.
20. Tobacco use within 3 months prior to screening.

21. For fresh sperm: male partners with non-obstructive azoospermia.
22. Any abnormal finding or condition deemed clinically significant by the Investigator on history, screening, physical examination, or pelvic examination that contraindicates pregnancy or the use of progesterone or a vaginal ring, including the presence of any vaginal or cervical abrasions/lesions.
23. Any condition the Investigator believes would interfere with the subject's ability to provide informed consent, to comply with trial instructions, or which might confound the interpretation of the trial results or put the subject at risk.

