6.3 Treatment with PVR

6.3.1 Visit 4: Initiation of Treatment with PVR

Treatment with PVR will be initiated one day after oocyte retrieval (Visit 4).

The following must take place at the visit:

- Vital signs
- Blood collection for assessment of:
 - Clinical chemistry and hematology parameters (*Note:* if Visit 4 occurs on a day where shipment to the central laboratory is not feasible, e.g. during the weekend, the subject will return to the site for blood collection on the next possible day)
 - Endocrine parameters (progesterone and estradiol)
- Assessment of vaginal hemorrhage
- Pelvic examination (documentation of presence and grade [intensity] of any pain, irritation, abrasions, or lesions on the cervix or vagina or vaginal adhesions, see [Appendix 2](#)).
- Dispensing of IMP: the first 4 PVRs will be distributed (PVR1, PVR2, PVR3 and PVR4). Subjects will be instructed in the proper method for PVR insertion and removal (see [Appendix 1](#)). The subject will insert PVR1 while at the trial site. Subjects will be allowed to remove the

PVR for up to 1 hour/day; this includes removal for sexual intercourse, although this is not necessary.

- Provide subjects with PVR diary and instructions on how to complete the diary. Subjects will be asked to fill out the diary at home for each PVR used and bring it to each subsequent visit.
- Provide subjects with bleeding log and instructions as to how to differentiate between vaginal discharge and bleeding (to capture the frequency and intensity of any bleeding). Subjects will be asked to fill in the bleeding log at home and bring it to each subsequent visit.
- Provide subjects with sanitary napkins. Subjects will be instructed to use only sanitary napkins provided by the trial site for any bleeding that occurs during the trial.
- Recording of use of any concomitant medication
- Recording of AEs

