7.3.5 Pelvic Examination and Pap Smear at Screening

A pelvic examination, including recording of baseline parameters in the pelvic examination page of the eCRF, will be conducted at screening to confirm the subject has no clinically significant gynecologic pathology or other conditions that could adversely affect pregnancy success.

In addition, a Pap smear will be performed at screening if not done in the previous 24 months. If done in the previous 24 months, the results must have been normal and a copy of the report must be filed in the subject's chart and recorded in the eCRF.

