9.9 Safety

9.9.1 General Considerations

Safety parameters will be evaluated for the ES and safety cohorts. Safety summaries will be presented by the 5 phases of the trial. These phases are defined as follows:

- Screening Phase: From the date of signing the informed consent through the day before the start of the oral contraceptive treatment.
- Suppression Phase: From the start of oral contraceptive treatment until the day before the start of the stimulation phase (start of MENOPUR treatment).
- Stimulation Phase: From the date of the first dose of MENOPUR through the day before the start of IMP.
- Treatment Phase: From the date of the first dose of IMP (PVR) through the end of the trial.
- Study Phase: From the date of the first dose of oral contraceptive through the end of the trial.

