### 10.3 Safety Laboratory Variables

Baseline for all laboratory analyses will be the values obtained at visit 4. If visit 4 is missing, then the last assessment prior to visit 4 will be used. Treatment-emergent laboratory data will include tests completed after the first dose of IMP through the residual time of drug effect. End of trial will include the last post-baseline observation during the trial.

Laboratory variables will be grouped under “Hematology”, “Clinical Chemistry” or “Urinalysis”.

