#### **10.4.3 Pelvic Examination**

A pelvic examination will be performed at screening, Visits 4, 7P, 8, 9, and 10 to document the presence and grade (intensity) of any pain, irritation, abrasions, or lesions on the cervix or vagina using standardized criteria, and the presence and grade (intensity) of any vaginal adhesions using standardized criteria. If any lesions or abrasions are found on the cervix or vagina or vaginal adhesions are noted, another examination will be performed 2-4 days later. The grade (intensity) for each type of assessment will be summarized by visit for the safety cohort. Furthermore, a shift table will be presented summarizing the change in grade (intensity) from Visit 4 to the End-of-trial, where the End-of-trial is defined to be the last assessment in the treatment phase.

An associated listing will also be produced.

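### The end value of the pelvic-examination shift table can be the Visit 4 baseline examination itself, so a woman with no later examination is counted as unchanged

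*Protocol*

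**What the plan says.** Both documents give the same rule. Protocol 9.9.7 tabulates the "change in grade (intensity) from Visit 4 to the End-of-trial, where the End-of-trial is defined to be the last assessment in the treatment phase". SAP 10.4.3 states that "a shift table will be presented summarizing the change in grade (intensity) from Visit 4 to the End-of-trial", and closes the interval with "where the End-of-trial is defined to be the last assessment in the treatment phase". Neither document limits the end value to an examination after Visit 4, and neither says what to do with a woman who has none.

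The treatment phase is defined in Protocol 9.9.1, and identically in SAP 1.1.1 and 10.1: "Treatment Phase: From the date of the first dose of IMP (PVR) through the end of the trial". Visit 4 is the first day of that phase. Protocol 6.3.1 places the first ring the day after oocyte retrieval and lists a graded pelvic examination at the same visit.

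For laboratory values SAP 10.3 is stricter: "End of trial will include the last post-baseline observation during the trial". SAP 10.3.5 puts the same restriction on vital signs. Both use Visit 4 as baseline.

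An earlier examination exists. Protocol 7.3.5 says that a pelvic examination, "including recording of baseline parameters in the pelvic examination page of the eCRF, will be conducted at screening". Exclusion 22 in Protocol 4.1.2 lists, among findings that keep a woman out, "including the presence of any vaginal or cervical abrasions/lesions". The shift table does not use the screening examination.

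**The concern.** Pain, irritation, abrasions, lesions and adhesions are the local findings of interest for a vaginal ring, and they bear on named secondary endpoints. This is the only planned table that follows pelvic grades within a woman.

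The definite fault is at the end of the interval. A woman who was never re-examined gives no information on change, yet the written rule puts her on the diagonal of the table as evidence of no worsening. That dilutes any proportion worsened.

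A lesser point concerns the start. The Visit 4 examination comes one day after a retrieval done under transvaginal ultrasound guidance. If it records a grade on some parameter, a later new finding of the same grade on that parameter appears as no change, and a lower one appears as improvement.

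**Working it through.** **Step 1. Is the baseline examination inside the treatment phase?** The Visit 4 examination and the first ring share a date (Protocol 6.3.1). The phase begins on that date, inclusive (Protocol 9.9.1). The candidates for the last assessment are therefore Visits 4, 7P, 8, 9 (or early withdrawal), 10 and any unscheduled examination. If nothing follows Visit 4, the last assessment is Visit 4 and the shift is from a grade to itself.

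**Step 2. The same woman under the laboratory rule.** Visit 4 is her baseline, she has no post-baseline observation, so she has no end value and no shift. The two rules treat identical missing data differently.

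**Step 3. Who could have no later examination?** The first scheduled one after Visit 4 is at 7P, 4 weeks + 3-4 days after retrieval. A woman who stops earlier, for example with a negative β-hCG at Visit 6, depends on the early-withdrawal and End-of-trial examinations. Protocol 3.5.6 requires both visits, and 6.3.8 and 6.4 include the examination. However, Protocol 4.4 says only that a woman who withdraws is advised to consider follow-up, and the Visit 6 stop rule (6.3.3) does not repeat the early-withdrawal instruction given at 6P, 7 and 7P.

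**Step 4. Illustration of size.** The plan states no figure for this table, so there is none to reproduce. All three rates below are assumptions:
- w: share of examined women with a new finding at the end value;
- b: share of those whose Visit 4 grade on the same parameter is already at or above the later grade;
- u: share of women with no examination after Visit 4.

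If these are independent, share shown as worsened = w(1-b)(1-u). Take N = 240 (Protocol 3.2; the safety cohort is at least as large as the mITT cohort) and w = 10%:

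| b | u | Shown as worsened | Women of 240 |
|---|---|---|---|
| 0 | 0 | 10.0% | 24.0 |
| 0 | 5% | 9.5% | 22.8 |
| 0 | 10% | 9.0% | 21.6 |
| 10% | 0 | 9.0% | 21.6 |
| 10% | 10% | 8.1% | 19.4 |
| 20% | 20% | 6.4% | 15.4 |

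The relative loss is 1 - 0.9 × 0.9 = 19% at b = u = 10%, 1 - 0.8 × 0.8 = 36% at b = u = 20%, and zero at b = u = 0.

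**Step 5. What each change recovers.** At b = u = 10%, 216 women are examined and 19.4 are shown as worsened.
- Restricting the denominator to examined women gives 19.4/216 = 9.0%, which removes the (1-u) factor.
- A table from screening would show 21.6/216 = 10.0%, provided that screening grades are 0 on that parameter and no stimulation or retrieval effect persists. That removes the (1-b) factor.

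**The case against.** The strongest reply is that the Visit 4 baseline is deliberate. It is the examination closest to ring start, it matches the laboratory and vital-sign baseline, and Protocol 6.3.1 lists it before insertion of the first ring (though it does not state the order). Screening can last up to 90 days and is followed by suppression and stimulation, so a shift from screening would charge their effects, and those of retrieval, to the ring. The baseline parameters in Protocol 7.3.5 serve eligibility and do not define the analysis baseline. This stands. A reader might infer that Visit 4 is the wrong baseline, and the documents do not support that.

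A reader might also infer that ring findings are masked in the trial's safety evidence. They are not. Grades are summarized by visit and listed, findings judged clinically significant after treatment start become adverse events (Appendix 2), and adverse events of special interest are tabulated by term, grade and seriousness. Masking in the shift table needs a Visit 4 grade at or above the later one on the same parameter, and Appendix 2 grades many parameters separately. A new finding after grade 0, or a later higher grade, still shows as worsening. The documents do not say how often retrieval leaves a graded finding, or that it does, so a large assumed b has no support. By-visit counts do not show within-woman change, however, and the adverse-event tables omit findings not judged clinically significant.

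Finally, one may say that a change from Visit 4 to End-of-trial plainly implies two examinations, and that few women will lack the second. The first is probably the intention, but the written definition says otherwise, and the same SAP includes the missing word for laboratory values and vital signs. The second is fair: only women who miss both required visits and any other examination are affected.

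**Conclusion.** The end-value rule is faulty as written in both documents: the baseline examination qualifies as the last assessment, and a woman not examined again is counted as unchanged. This rests on the definitions alone.

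The effect always dilutes the share worsened, and it should be small if the required visits take place. The choice of Visit 4 as baseline is sound, and its timing after retrieval justifies a supplementary table but no replacement. The size of either effect cannot be determined, because the documents give none of w, b or u. The illustrated losses follow from assumed values and independence. The point is confined to one descriptive table and does not touch the primary endpoint or the sample size.

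**What to change.** In Protocol 9.9.7 and SAP 10.4.3:

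1. Define the end value as the last pelvic examination, scheduled or unscheduled, made after Visit 4 and within the trial.
2. Show women with no such examination on a separate line, outside the shift denominator.
3. Keep the Visit 4 shift table, and add a supplementary one from the screening examination to the same end value.

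The first two changes are wording and one table line. The third is one extra table from data already collected. Its small downside is that a change from screening also contains stimulation and retrieval effects, so it should be labelled that way and read beside the Visit 4 table.
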